2.4 Formal planned analyses

2.4.1 Primary analysis

The primary analysis will be performed when all patients have completed the double-blind treatment epoch (Week 24 [EOT] assessments regardless of treatment completion or premature discontinuation of treatment/study in the 24-week treatment epoch). The [REDACTED] biostatistics team will be unblinded at patient level to conduct the primary analysis (whereas selected members of the Novartis global team will only be unblinded at group level). Patients, site personnel and country investigators will remain blinded until the final database lock. An independent global clinical person will have access to individual randomization codes after the primary analysis.

Assignment and authorization (per [REDACTED] internal procedure) of patients to the different analysis sets, [REDACTED], will be performed prior to the unblinding of the treatment code and start of the primary analysis. At the time of the primary analysis, subgroups with a stratification level containing less than five patients will be suppressed and only the count (n) will be displayed. In addition, minimum and maximums in tables will be suppressed. These measures are to avoid potential unblinding of the selected members of the Novartis global team. Details of the level of unblinding, including identification of unblinded contact personnel in both teams will be included in a separate unblinding plan created by the [REDACTED] biostatistics team.

All data will be included in the data transfer for the primary analysis. By-visit data up to and including Week 24 will be cleaned at that time whilst other data such as AEs and concomitant medications (CM) will be as clean as is feasible, following data checks. In addition, at the time of the primary analysis, some patients may still be ongoing or may even have completed the post-treatment follow-up epoch. As such, by-visit data following Week 24 will also be included in the data transfer, as relevant although limited queries may still be outstanding and it is accepted that the data are not in clean, locked state. All AE and CM data available at the time of the primary analysis will be included in the data transfer. The [REDACTED] biostatistics team will ensure that the state of all data received in the data transfer at the time of the primary analysis is as expected.

Unless otherwise specified, data will be summarized relative to the number of patients who entered the respective epoch (number of patients “at risk”). At the time of the primary analysis number of patients “at risk” comprises:

- Treatment epoch: Patients assigned to the relevant analysis set (for example safety [SAF] or full analysis set [FAS]) regardless of study status, implying all patients entering the treatment epoch and who received at least one infusion of study drug.
- Post-treatment follow-up epoch:
 - Patients who completed treatment but are ongoing in the post-treatment follow-up epoch or who have discontinued during the post-treatment follow-up epoch.
 - Patients who prematurely discontinue treatment within the defined 24-week treatment epoch and who then continue study participation as part of the planned 4-week post-treatment follow-up.
 - Patients who completed the treatment epoch and the post-treatment follow-up epoch (study completed at the time of the primary analysis).

The same convention in view of patients entering the post-treatment follow-up epoch will apply at the time of the final update analysis.

It is expected that efficacy analyses based on the 24-week treatment epoch will be considered final at the time of the primary analysis. In view of ongoing cleaning activities on AE and CM data, safety analyses related to these data, will not be final. For the post-treatment presentations, where both the treatment epoch and post-treatment follow-up epoch are presented, analyses will also not be considered as final at the primary analysis and will only be complete at the time of the final update analysis.

2.4.2 Final update analysis

Additional efficacy and safety data will be recorded from Week 24 to Week 48. During the post-treatment follow-up epoch patients, the Novartis global study team and investigative centers will still be blinded to the treatment received in the treatment epoch. When all patients have completed the post-treatment follow-up epoch (Week 48 [EOS] assessments regardless of study completion or premature discontinuation), the database will be finally locked (clean state of all data expected) and the final update analysis will be performed. Any data collected in the post-treatment follow-up epoch as indicated in the programming notes in RAP Module 7 (CSR Deliverables) will be revisited, finalized and authorized at the time of the final update analysis.

At the time of the primary analysis (Week 24), any additional efficacy and safety data available in the post-treatment follow-up epoch, will be summarized in a similar manner as planned for the final update analysis, i.e. relative to the number of patients with data collected in the post-treatment follow-up epoch as described in [Section 2.4.1](#) (Primary analysis).

The same convention in view of patients entering the post-treatment follow-up epoch will apply at the time of the final update analysis.

Furthermore, the same data handling conventions as described in [Section 2.3](#) (Treatment pooling and data handling of pre-amendment 2) will be applied with regards to treatment-emergent and concomitant definitions.

2.5 Presentation

Unless otherwise specified, data will be presented as detailed in [Section 3.2](#) (Precision and summary statistics).

Relevant raw and derived data will also be presented in by-patient data listings. All by-patient data listings will be sorted by treatment group, with Japan ordered first and patient if not indicated otherwise. In by-patient data listings based on all enrolled patients, patients not randomized (with the exception of re-screened and subsequently randomized patients) will be sorted last as part of a “Not Randomized” treatment group.

For re-screened patients, patient numbers will be linked and both sets of data will be presented in by-patient data listings, where relevant (see all enrolled analysis set, as referenced in [Section 2.7](#) [Analysis Sets] for more details). For analysis purposes, only data pertaining to the randomized patient number will be used as identified by means of a flag variable in the relevant by-patient data listings.

Data recorded in free text fields will not be modified by the [REDACTED] biostatistics team and will be presented by the text “Specification (eCRF)” as indicated by the investigator on the relevant eCRF.

In this document, where relevant, “across all four treatment groups combined” refers to the addition of a “Total” column. Similarly, “across active bimagrumab treatment groups combined” refers to the addition of an “Active Total” column based on the type of presentation:

[figure not shown]

[figure not shown]
[figure not shown]

- “Active Total: Efficacy”: For efficacy presentations it will include all active treatment groups, except for the bimagrumab 70 mg treatment group.
- “Active Total: Safety”: For safety presentations it will include all active treatment groups, including the bimagrumab 70 mg treatment group.

In the same manner “overall” refers to over all levels of stratification of the relevant planned subgroup presentation of the data.

2.6 Subgroups

Table 2.2 Subgroups

Subgroup	By-group Presentations	Covariates

 • Region (geographical): 
 ○ Japan (Patients from centers in Japan). ○ Non-Japan (Patients from centers not in Japan). 	
 • Patient disposition. • Patient demographics and other Baseline characteristics (with the exception of general medical history, cardiovascular history, tobacco usage, [REDACTED]). • Study drug administration. • Primary and secondary efficacy. • Falls during the study. [REDACTED] • Physical activity. • Other DXA assessments (leg LBM [kg], [leg], [REDACTED]). • Adverse events. • Vital signs. [REDACTED] • Laboratory assessments (hematology, clinical, immunochemistry and urinalysis labs) 	
Primary and secondary efficacy.

 • Treatment Date: 
 ○ Early (≤ 21 days) (Patients randomized 21 days or less from their hip fracture surgery date). ○ Late (> 21 days) (Patients randomized greater than 21 days from their hip fracture surgery date). 		
Primary and secondary efficacy.

Subgroup	By-group Presentations	Covariates
	
 • Primary and secondary efficacy. • Other DXA assessments (total fat body mass [kg], [whole body],   ). • Falls during the study.   . • Vital signs (BMI). 	

 • Fracture Fixation Type: 
 ○ Internal (screws only, intramedullary [nails] and extramedullary fixation [plate, combinations]). ○ Arthroplasty (hemiarthroplasty or total hip arthroplasty). 
As recorded in the Hip fracture – perioperative data eCRF.
	
 • Primary and secondary efficacy. • Falls during the study.  . 	Secondary efficacy.

 • History of Falls (12 months): 
 ○ Yes. ○ No (none). 
The number of falls in the past year (12 months) prior to Screening is recorded in the Fall history eCRF. If number of falls in the past year (12 months) > 0 then the history of falls (12 months) is considered as “Yes”, otherwise “No (none)”.
	
 • Primary and secondary efficacy. • Falls during the study.  . 	Secondary efficacy.

 • Use of Mobility Aids Prior to Hip Fracture (3 months): 
 ○ Yes. ○ No (none). 
Use of Mobility Aids Prior to Hip Fracture (3 months) classified as recorded in the Baseline physical activity eCRF: “Within the last three months prior to hip fracture, what type of assisting device (referred to as mobility aid in this document) did the patient need for his/her daily activity?” If a mobility aid is recorded in the eCRF then the Use of Mobility Aids Prior to Hip Fracture (3 months) is considered as “Yes”, otherwise “No (none)”.
	
 • Primary and secondary efficacy. • Falls during the study.  . 	Secondary efficacy.

Subgroup	By-group Presentations	Covariates

 • 25OH Vitamin D at Screening: 
 ○ < 30 nmol/L (< 12 ng/mL). ○ ≥ 30 nmol/L (≥ 12 ng/mL). 	
 • Primary and secondary efficacy. • Falls during the study. • [REDACTED] 	

 • Amendment: 
 ○ Pre-amendment 2. ○ Post-amendment 2. 	
 • Primary and secondary efficacy. • Study drug administration. 	

[REDACTED]. DXA: Dual energy X-ray absorptiometry. eCRF: Electronic case report form. [REDACTED]. LBM: Lean body mass. SPPB: Short physical performance battery. SD: Standard deviation. Primary efficacy variable: Total LBM (kg). Secondary efficacy variables: Derived gait speed (m/sec) and total SPPB score. Subgroup presentation: First level of stratification will be “Overall” implying over all levels of stratification of the relevant planned subgroup presentation of the data.

2.7 Analysis sets

Assignment of patients to the different analysis sets detailed below will be performed prior to the unblinding of the treatment code and start of the primary analysis.

All enrolled analysis set: All enrolled patients who provided informed consent (as recorded in the Informed consent eCRF), will be deemed as the all enrolled set, as such, accounting for all enrolled patients. Patients who are re-screened and randomized will be counted only once, based on their re-screening record. Patients who are re-screened but who eventually are not randomized will also be counted once. Enrolled patients, who were not randomized (with the exception of patients re-screened and subsequently randomized) will be sorted last as part of a “Not Randomized” treatment group in by-patient data listings based on the all enrolled analysis set. Linked records will be sorted together using patient numbers and informed consent date (to order chronologically).

The following analysis sets are defined for primary and final update analysis purposes as detailed in this RAP:

Randomized analysis set: All randomized patients, regardless of whether the patient received study drug. This set will consist of all patients who provided informed consent (as recorded in the Informed consent eCRF) with a randomization number and a completed randomization date as per IRT.

Safety (SAF) analysis set: The SAF analysis set will consist of all patients who received at least one infusion of study drug. Patients will be analyzed according to the treatment actually received. If a patient received only part of the infusion (i.e. study drug infusion permanently discontinued), the patient will be regarded as having received study drug infusion and will be assigned to the SAF analysis set. At least one infusion, or part of an infusion (as recorded in the Dosage administration record – infusion eCRFs) will be used to assign patients to the SAF analysis set.

Full analysis set (FAS): The FAS will consist of all randomized patients who received at least one infusion of study drug. Patients who are randomized due to erroneous use of the IRT system and who did not receive at least one infusion of study drug will be excluded from the

FAS. Following the intent-to-treat principle, patients will be analyzed according to the treatment they were assigned to at randomization.

The following subsets of patients will be identified for inclusion in the proposed primary and secondary efficacy sensitivity analyses ([Section 2.10.1](#) [Analysis of the primary efficacy variable] and [Section 2.10.2](#) [Analysis of secondary efficacy variables], respectively):

- Total LBM Week 24 Completers FAS Analysis Subset: Patients who have a windowed visit Week 24 total LBM assessment (kg) (primary endpoint) having completed treatment (Week 24 [EOT]).
- SPPB Week 24 Completers FAS Analysis Subset: Patients who have a windowed visit Week 24 SPPB assessment (secondary efficacy endpoint) having completed treatment (Week 24 [EOT]).
- Gait speed Week 24 Completers FAS Analysis Subset: Patients who have a windowed visit Week 24 gait speed assessment (secondary efficacy endpoint) having completed treatment (Week 24 [EOT]).
- SPPB Week 48 Completers FAS Analysis Subset: Patients who have a windowed visit Week 48 SPPB assessment (secondary efficacy endpoint) having completed both the treatment (Week 24 [EOT]) and post-treatment follow-up (Week 48 [EOS]).
- Gait speed Week 48 Completers FAS Analysis Subset: Patients who have a windowed visit Week 48 gait speed assessment (secondary efficacy endpoint) having completed both the treatment (Week 24 [EOT]) and post-treatment follow-up (Week 48 [EOS]).

Per Protocol (PP) analysis set: The PP analysis set will include all FAS patients without major deviations from the protocol procedures at the time of the primary analysis. Major protocol deviations and the definition of the PP analysis set will be identified and finalized based on blinded review of the data, prior to the data extraction for the primary analysis and unblinding of the treatment code.

Modified Per Protocol (PP) analysis set: The Modified PP analysis set will include all FAS patients without a major deviation from the protocol procedures occurring after Week 24 and will be used at the time of the final update analysis. Major protocol deviations and the definition of the modified PP analysis set will be identified and finalized, prior to the data extraction for the final update analysis.

For the definitions of major protocol deviations see [Section 3.10](#) (Protocol deviations).

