9.2 Analysis sets

The Full Analysis Set (FAS) used for all efficacy analyses will consist of all randomized patients who received at least one dose of investigational treatment. Patients will be analyzed according to the treatment they were assigned to at randomization. Patients who entered the study before Amendment 2 will be pooled with fixed-dose patients as follow: bimagrumab 3 mg/kg patients will be analyzed as member of the 210 mg group, bimagrumab 10 mg/kg patients will be analyzed as member of the 700 mg dose group.

The safety (SAF) Analysis Set will consist of all patients who received at least one dose of study medication. Patients will be analyzed according to the treatment received. Patients who entered the study before Amendment 2 will be pooled with fixed-dose patients as detailed for the FAS.

Per-protocol (PP) Analysis Set will include all FAS patients who complete the study without major deviations from the protocol procedures. Major protocol deviations and the definition of the PP set will be identified and finalized based on blinded review of the data, prior to the data extraction for the primary analysis (EoT) and the global study team group level unblinding.

For patients who entered the study before Amendment 2 and have been treated for more than 6 months, data collected after the Week 24 visit will be listed.

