3.10 Protocol deviations

The process by which reasons for exclusion are identified involves the creation of a protocol deviation edit specifications document, listing all potential deviations (identified programmatically using codes, per data collected). Using this list, potential deviations are identified by checking the data during the clinical conduct of the study. The identified potential deviations are then shared with the Novartis clinical team. The team meets to discuss the list on a monthly basis. Protocol deviations which can be identified programmatically will be done using validation procedures within OC/RDC. Once these discrepancies are confirmed to be protocol deviations, the system will automatically load these records into the DV (Protocol Deviations) domain. Potential protocol deviations identified manually will be proposed by the Study Lead (or Field Monitor) and cCRA and entered as discrepancies in the EDC database; based on the site's response, the Study Lead will confirm whether the protocol deviation is CSR reportable. These PDs will also be loaded into the DV domain by Novartis.

Once confirmed by the Novartis clinical team, the [REDACTED] biostatistics team will use the identified and confirmed list of protocol deviations from the DV domain as the potential reasons to exclude patients from the respective analysis set(s). Should the domain contain any of the below criteria, identified programmatically (by means of the codes which are assigned) the impact of the criteria will be considered major and summarized as such in the CSR.

Exceptions to the following inclusion/exclusion are considered as major protocol deviations and will lead to exclusion of patients from the relevant analysis sets:

Protocol Deviation Category: Selection criteria not met

Inclusion/Exclusion Criteria Number	Inclusion/Exclusion criteria text
Inclusion 1	Written informed consent must be obtained prior to any assessment is performed.
Inclusion 2	Patient must have had surgical fixation or arthroplasty of the hip fracture (Association for the Study of Internal Fixation [AO] Classification 31 A-C [AO Foundation 2013]) as confirmed by radiography.
Inclusion 3	Patient must be mentally competent, to have scored at least ≥ 21 on the Folstein Mini Mental State Examination (MMSE).

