Exclusion 12	Ongoing corticosteroid use or history of systemic corticosteroid use for at least 3 months (in the last year) prior to randomization at a daily dose greater than or equal to 10 milligram (mg) prednisone equivalent.
Exclusion 13	Currently enrolled in, or discontinued within the last 30 days (or 5 half-lives, or until PD effect is expected to return to Baseline, whichever is longer or longer if required by local regulations) from a clinical trial involving an investigational drug or off-label use of a drug, or are concurrently enrolled in any other type of medical research judged to be scientifically or medically incompatible with this study.

The following protocol deviations are considered as important and will lead to exclusion of patients from the analysis sets as decided by the Novartis clinical team during their monthly discussions:

Protocol Deviation Category	Protocol deviation description
Patient not withdrawn as per protocol	Patient not discontinued from treatment after informed consent withdrawn.
	Patient not discontinued from treatment after emergency/accidental unblinding.
	Patient not discontinued from study despite missing two infusions at any time during the treatment epoch.
Treatment deviation	Patient received study drug without being randomized into study.
	Patient randomized in error and study medication was given.
	Patient received wrong dose or strength of the study drug.
	Patient received expired study drug.
	Patient received wrong study medication (e.g. placebo instead of active drug).

Protocol Deviation Category	Protocol deviation description
Prohibited concomitant medication	Patient took a prohibited medication while in the study, however was not discontinued from the study.

The following protocol deviation terms (in the DV domain) will lead to the exclusion from the PP analysis set as decided by the Novartis clinical team:

Protocol deviation description
Mishandling of study drug medication at the site or by the patient (e.g. storage condition not respected) and patient took drug.
Subject received wrong dose or strength of the study drug

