The final analysis set assignment [REDACTED] and identified major reason(s) for exclusion of patients, based on the confirmed list in the DV domain, from one or more of the analysis sets will be confirmed by Novartis prior to study unblinding at the time of the primary analysis. Following this, at the time of the primary analysis, routine study unblinding of the [REDACTED] biostatistics team may commence.

Treatment deviations (by identifying discrepancies between randomized treatment assignment and actual treatment received, using information in the DV domain and other domains provided by Novartis [randomization schedule and kit numbers]) and finalizing the [REDACTED] analysis set (with review by Novartis) will be determined after study unblinding of the treatment code and before the start of the primary analysis. Both treatment deviations and the [REDACTED] analysis set will be reviewed and confirmed by Novartis and an authorization form will be completed per [REDACTED] internal procedure. This information will be passed on to the medical writer to support development of the CSR.

Patients with treatment deviations, if identified, will be handled in the following way, in terms of the analyses:

- For Safety, patients will be analyzed per actual treatment received.
- For FAS, patients will be analyzed per randomized treatment assignment.
- For PP, they will be excluded.

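### As written, the Modified PP set in SAP 2.7 takes back every patient whose only major deviations occurred by Week 24

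*SAP*

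**What the plan says.** Protocol 9.2 has one per-protocol set: FAS patients who "complete the study without major deviations from the protocol procedures". Its membership is to be settled by blinded review before the data extraction for the primary analysis. The protocol defines no modified version.

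SAP 2.7 has two sets. For the primary analysis: "The PP analysis set will include all FAS patients without major deviations from the protocol procedures at the time of the primary analysis". This set keeps the blinded review. For the final update analysis: "The Modified PP analysis set will include all FAS patients without a major deviation from the protocol procedures occurring after Week 24". For this second set the SAP says that the major deviations and the "definition of the modified PP analysis set will be identified and finalized, prior to the data extraction for the final update analysis". That sentence does not mention blinded review.

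SAP 3.10 lists the deviations. Failures of the listed entry criteria are "considered as major protocol deviations and will lead to exclusion of patients from the relevant analysis sets". Other listed items include "Patient not discontinued from study despite missing two infusions at any time during the treatment epoch" and "Patient took a prohibited medication while in the study, however was not discontinued from the study". For patients whose received treatment differs from the assigned one, SAP 3.10 gives a rule for each set. The per-protocol rule is "For PP, they will be excluded"; Modified PP is not mentioned.

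**The concern.** A per-protocol set at the final update should contain patients who kept to the protocol throughout. A cumulative set would be the PP set minus anyone with a new major deviation in follow-up. The SAP's wording gives something else: it looks only at deviations after Week 24 and ignores those before it. A patient who failed an entry criterion or received the wrong study drug is removed from PP and then returns in the later set. Any final-update analysis run on that set would include the patients a per-protocol set is meant to leave out, and it could not be read as a continuation of the Week 24 per-protocol analysis, because the population would have changed in the wrong direction.

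**Working it through.** No power, sample size or alpha figure is involved, so the check compares the two definitions and then the deviation list.

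**Step 1: the two definitions as sets.**

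- PP = FAS minus patients with any major deviation known at the primary analysis.
- Modified PP = FAS minus patients with a major deviation occurring after Week 24.

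The primary analysis takes place once all patients have reached Week 24 or left, so deviations up to Week 24 are taken as known by then.

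| Timing of major deviations | PP | Modified PP as written | Cumulative set |
|---|---|---|---|
| None | in | in | in |
| By Week 24 only | out | **in** | out |
| After Week 24 only | out if already known at the primary analysis, otherwise in | out | out |
| Both | out | out | out |

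The second row is the problem. The fourth row shows its limit: a patient with both an early and a late major deviation stays out.

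**Step 2: which listed deviations can occur after Week 24.** From SAP 3.10:

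- Entry criteria: 3 inclusion + 13 exclusion = 16 items. All date from screening or randomization, so none can occur after Week 24.
- Not withdrawn as required: 3 items. Two concern failure to stop study treatment and the third is tied to missed infusions in the treatment epoch. The last planned infusion is at Week 20 (Protocol 3.1), so these normally arise by Week 24.
- Treatment deviations (5 items) and the PP-specific terms (2 items: drug mishandling, and wrong dose, which also appears among the 5). All concern dosing, so they too normally arise by Week 24.
- Prohibited medication: 1 item. Protocol 5.5.8 bars these treatments through Week 48, so this deviation can occur in follow-up.

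That is 16 + 3 + 5 + 2 + 1 = 27 entries, or 26 distinct ones with wrong dose counted once. Prohibited medication is the main one that can arise after Week 24. The dosing and withdrawal items could do so in pre-amendment 2 patients treated beyond 24 weeks, at most the 14 enrolled (SAP 2.3). These are counts of deviation types, not of patients.

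**Step 3: does any other text carry the exclusions forward?** SAP 2.7 builds both sets from the FAS. SAP 2.8.1 tabulates exclusions from the SAF, FAS and PP sets without naming Modified PP. SAP 3.10 names only PP in its treatment-deviation rule. SAP 2.14, the list of changes from the protocol, does not mention the new set. No sentence makes Modified PP a subset of PP.

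**Step 4: who decides membership, and blind to what?** SAP 2.7 opens by saying that sets are assigned before unblinding. That cannot cover Modified PP, whose follow-up deviations have not all happened by then. At the primary analysis the biostatistics team is unblinded at patient level (SAP 2.4.1), while Protocol 5.4 and SAP 2.4.1 limit the sponsor's study team to group-level results. Deviations are identified by pre-specified codes or raised by the study lead or monitor, and are confirmed by the sponsor's clinical team (SAP 3.10). The biostatistics team then uses the confirmed list. Protocol 8.3 is looser: it says treatment codes go to the sponsor's global study team at the primary analysis.

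**The case against.** The best defence is that a cumulative set was intended. SAP 3.10 sends failed entry criteria out of the relevant analysis sets, in the plural; the set is named as a modified PP set; and its definition is still to be finalized before the final update extraction. This makes loose drafting more likely than a deliberate choice to readmit. But a general reference to relevant sets does not override an explicit definition, and a programmer following SAP 2.7 would not build a cumulative set.

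It can also be said that Protocol 9.2 needed adapting, because a whole-study criterion fixed before the Week 24 analysis cannot capture later deviations. That is correct: having a second set is reasonable, and only its definition is at fault.

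Three stronger readings are tempting, and the documents do not support them.

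- A reader might infer that everyone excluded from PP returns. Patients who also have a major deviation after Week 24 do not, and prohibited medication begun early may continue past Week 24.
- A reader might infer that the Week 48 per-protocol results are compromised. No visible section specifies such an analysis. The only per-protocol analysis described repeats the primary analysis of total LBM on the ordinary PP set (SAP 2.10, 2.10.1.6). DXA after Week 24 is only listed (SAP 2.3). The secondary sensitivity analyses use the completer subsets (SAP 2.10.2.4). Use in redacted text or in RAP Module 7 cannot be seen.
- A reader might infer that membership will be decided with knowledge of treatment. The SAP 3.10 criteria are pre-listed and applied by the sponsor's clinical team, and SAP 2.4.2 keeps the global study team blinded to treatment received during follow-up. What stands is narrower: blinded review is stated for PP and omitted for Modified PP, and Protocol 8.3 does not agree with Protocol 5.4 on access to codes.

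**Conclusion.** The point holds as a wrong rule, not merely a missing detail. Read as written, Modified PP includes every FAS patient whose only major deviations occurred by Week 24, and this covers most of the deviation types in SAP 3.10.

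Its reach is limited. The primary analysis, its per-protocol repeat and the alpha-controlled secondary tests do not use this set. The SAP says only that the set will be used at the final update. The number of patients affected is unknown and could be small. The conclusion assumes that the SAP 2.7 sentence would be programmed literally and that no unseen document corrects it. It should be corrected before the final update extraction.

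**What to change.** Amend SAP wording in four places:

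1. SAP 2.7: define Modified PP as FAS patients with no major deviation at any time through end of study, that is, all PP exclusions carried forward plus any new major deviation after Week 24.
2. SAP 3.10: extend the exclusion of patients with treatment deviations from PP to Modified PP.
3. SAP 2.7: restore blinded review for this set, using the SAP 3.10 criteria applied by staff without patient-level treatment codes.
4. SAP 2.14: list the set as a change from Protocol 9.2.

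The cost is a few sentences and one line of set derivation. No new data are needed, and no primary or alpha-controlled analysis changes.
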